9.4.5.2 Phase II – Face-to-Face Developmental Testing at 3.5-5.0 Years of Age

When the children are at least 3.5 years of age but not yet 5.0 years of age, a subset will then be evaluated through a single set of direct assessments completed in the **subject's/child's** home setting, as well as an age appropriate set of maternally completed questionnaires. Preference will be given to the assessment of children exposed prenatally for the longest durations and children in each of the comparison groups who are of similar age. Longer duration exposures should improve the ability to assess risks because brain development continues throughout prenatal development and may be vulnerable to drug exposure beyond the first trimester. Direct assessment will be conducted using the Wechsler Preschool and Primary Scale of Intelligence-IV (WPPSI-IV). This standardized (Z-score), norm-referenced measure provides an evaluation of the child's general mental ability, verbal and non-verbal abilities, as well as

processing speed. The mother or primary caregiver will complete 1 questionnaire about the child’s development, the Behavioral Assessment Scale for Children (BASC-III), and questionnaires about her own functioning, the **CES-D**, the **PSI**, and the **Edinburgh Postnatal Depression Scale (EDPS)**. These questionnaires will provide additional information about the child’s social and emotional development in the family context. Additionally, a direct evaluation of the mother or primary caregiver’s cognitive functioning will be made using the Wechsler Abbreviated Scale of Intelligence (WASI-II). Understanding the cognitive level of the mother will facilitate accuracy of interpretation of children’s scores and any group differences.

Face-to-face assessments will be made until a sample size of 40/group (cohorts 1-3) has been reached. At this sample size, statistical power (0.80) will allow confidence in judgments of group differences of SD in primary score endpoints.

Table 2. Postnatal Developmental Screening and Evaluation, Phase I (16 Months and 17 Months 30 Days of Age) & Phase II (3.5-5.0 Years)

Age	Measure	Description

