9.5 Study Size

An enrollment total of 75 in the exposed group and 150 in each of the 2 comparison groups after 10 years is anticipated. Given that these numbers assume the prevalence of exposure is sufficient to support recruitment of these numbers, the feasibility of achievement will be re-evaluated at each annual interim review of the data.

Based on previous experience with MotherToBaby/OTIS Pregnancy Studies, we estimate that subjects will be an average of 7-10 weeks post-LMP at the time of enrollment. Given this mean gestational timing at enrollment, the anticipated spontaneous abortion/stillbirth rate is 10%, the estimated elective abortion rate is 5%, and the estimated lost to follow-up rate is 5%. This results in an estimated 71 observable pregnancies of which 60 are estimated to result in live births in cohort 1 (exposed group), and an estimated 142 observable pregnancies of which 120 are estimated to result in live births in cohorts 2 and 3 (control groups).

Baseline rates of major structural **birth** defects, spontaneous abortion, premature delivery, and small for gestational age, as well as the standard deviation for mean birth weight of full-term infants were based on previous MotherToBaby/OTIS studies and on general population data (Table 3). With the sample size estimated above, at $\geq 80\%$ power, alpha of 0.05, two-tailed tests of significance (except as noted below for pattern of minor structural **birth** defects), and each comparison group independently compared to the exposed group, the minimum effect sizes detailed in Table 3 will be detectable.

With respect to the evaluation of minor malformations, the strength of this study design is in the ability to examine the data for a pattern of minor and/or major structural **birth** defects, given that the known human teratogens are typically associated with a pattern as opposed to isolated major **structural** birth defects. A baseline prevalence estimate of 1% has been used for a specific pattern of minor **structural birth** defects. The RR detectable with this sample size is 10.0. This represents a 10% birth prevalence of a specific pattern (ie, approximately 6 children in the exposed sample), which is comparable to the birth prevalence of a specific pattern in other known human teratogens of moderate risk such as the anticonvulsant medications.

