For the primary outcome, the study is powered to detect that the Evolocumab-Exposed group has a 3.8-fold (or greater) risk of all major **structural** birth defects combined relative to the risk in the primary comparison group. This level of risk for teratogenicity is below that observed for other, but not all, agents deemed teratogenic. Importantly, known human teratogens tend to be associated with increased risks for specific patterns of birth defects and are not associated with increased risks for any and all major **structural birth** defects. For this reason, the analysis of the primary outcome, combined with evidence of a cluster or pattern of defects, provides the best ability for evaluation of teratogenic risk.

Table 3. Sample Size and Power for a Specified Effect Size Based on Minimal Sample Size^a

Outcome	N in Cohort 1	N in Cohort 2 or 3	Baseline Rate	RR	Power ^b
Major structural birth defects ^c	71	142	4% ^d	3.8	84%
Specific pattern of 3 or more minor structural birth defects	60	120	1% ^e	10.0	71% ^f
Spontaneous abortion/stillbirth	71	142	10% ^g	2.5	88%
Preterm delivery	60	120	9% ^h	2.8	85%
SGA	60	120	10% ⁱ	2.6	80%
Small for age (postnatal growth deficiency)	46	108	10%	2.8	82%
Neurodevelopmental outcomes (Phase II)	40	40	--	0.5 SD ^j	80%
Inadequate immune response (via IgG tetanus antibody status)	60	120 ^k	20% ^l	2	82%

Definitions: Ig = immunoglobulin; RR = relative risk; SGA = small for gestational age.

^a Software used to calculate power and effect size: OpenEpi v3 (Dean et al, 2015).

^b Based on Fisher's Exact Test or chi-square, two-tailed, alpha 0.05, except for specific pattern of 3 or more minor anomalies as noted below.

^c Primary endpoint.

^d Baseline rate in comparison group based on 4.1% in statin exposed (Winterfeld et al, 2013).

^e Baseline rate in comparison group expected to be 0-1% based on no evidence of a pattern.

^f Based on one-tailed Fisher's Exact Test, alpha 0.05.

^g Baseline rate based on 13.6% in statin exposed (Winterfeld et al, 2013) and 4.4% (Chambers et al, 2013) (rate influenced by gestational time of enrollment).

^h Baseline rate based on 16.1% (Winterfeld et al, 2013) and 6.2% (Toleikyte et al, 2011).

ⁱ Baseline rate based on 5.0% for low birth weight defined as < 5th centile which translates to 10% for SGA defined as < 10th centile (Toleikyte et al, 2011).

^j Minimum detectable difference calculated for neurodevelopmental outcomes as a continuous variable (instead of RR for categorical variables).

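### Table 3 claims 80% power for a 0.5 SD Phase II neurodevelopment difference with 40 children per group; the stated inputs give about 60%, and 80% power needs about 0.63 SD

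*Protocol*

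**What the plan says.** Section 9.4.5.2 sets the size of the face-to-face testing: "Face-to-face assessments will be made until a sample size of 40/group (cohorts 1-3) has been reached". It then states the power: "At this sample size, statistical power (0.80) will allow confidence in judgments of group differences". In the text at hand no number stands before "SD" in the rest of that sentence. It may have been lost when the PDF was read, and it is not counted as an error here.

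The effect size is in section 9.5. The Table 3 row reads "Neurodevelopmental outcomes (Phase II) 40 40 -- 0.5 SD ^j 80" (percent). Footnote j describes the 0.5 SD: "Minimum detectable difference calculated for neurodevelopmental outcomes as a continuous variable (instead of RR for categorical variables".

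The test conditions are also in section 9.5. The text before the table sets "alpha of 0.05, two-tailed tests of significance", compares each comparison group independently with the exposed group, and says that the Table 3 effects are detectable at 80% power or more. Footnote b repeats the two-tailed 0.05, "except for specific pattern of 3 or more minor anomalies as noted below", so the neurodevelopment row is two-tailed. Section 9.7.2.1 plans no adjustment for multiple testing, so alpha stays at 0.05 for each comparison.

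**The concern.** The protocol itself states the group sizes, effect size, alpha, sidedness and power for this row, so nothing is left for a statistical analysis plan to supply. Forty per group is well short of what a half-SD difference usually needs at 80% power.

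Phase II is the protocol's only direct cognitive testing of the children, and section 9.4.5.2 stops that testing once 40 per group is reached. The power figure therefore supports a stopping size. If it is wrong, a true half-SD difference would be missed about 4 times in 10 in a given comparison, where the table implies 2 in 10. A reader relying on Table 3 would give a non-significant Phase II result more weight than it can bear.

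**Working it through.** **Inputs**

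- n = 40 exposed and 40 in each comparison group (section 9.4.5.2; Table 3). These are assessed children, so no dropout allowance applies.
- Difference d = 0.5 in SD units (Table 3, footnote j).
- Alpha 0.05, two-sided, each comparison group tested separately (section 9.5).
- Stated power 80% (Table 3; 0.80 in section 9.4.5.2).
- Assumption: a two-sample comparison of means. Footnote b names Fisher's exact and chi-square tests, which do not fit a continuous score.

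**Attempt to reproduce the 80%**

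Standard error of the difference in SD units: √(1/40 + 1/40) = √0.05 = 0.2236.

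Standardised effect: 0.5 / 0.2236 = 2.236.

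Normal approximation: power = Φ(2.236 − 1.960) = Φ(0.276) = 60.9%.

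Noncentral t, 78 degrees of freedom, critical value 1.991, noncentrality 2.236: power = 59.8%.

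The stated 80% does not reproduce. The shortfall is about 20 percentage points.

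**Difference detectable with 80% power at 40 per group**

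Normal: (1.960 + 0.842) × 0.2236 = 0.626 SD. The t-test solution is 0.634 SD.

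**Children needed for 80% power at 0.5 SD, equal groups**

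Normal: 2 × (1.960 + 0.842)² / 0.5² = 62.8, so 63 per group. The t-test needs 64.

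**Could another reading give 80%?** (t-test unless noted, 0.5 SD)

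| Reading | Power |
|---|---|
| One-sided 0.05, 40 vs 40 | 71.6% |
| Both comparison groups pooled, 40 vs 80 | 72.6% |
| 40 vs 108 | 76.5% |
| 40 vs 120 | 77.7% |
| Three-group ANOVA, one group shifted by 0.5 SD | 62.1% |
| Two-sided alpha 0.15, 40 vs 40 | 78.3% |
| Two-sided alpha 0.20, 40 vs 40 | 82.7% |
| One-sample test of 40 children against a norm | 86.9% |

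Only the last two rows pass 80%, and both depart from the stated plan. If the sentence in section 9.4.5.2 meant a full SD, power would be about 99%, so that reading does not give 0.80 either.

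**Covariate adjustment**

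The share of outcome variance a covariate would have to explain is 1 − (0.5 / 0.634)² = 0.38, a correlation of about 0.62. The protocol states no such assumption for this row.

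**The case against.** The strongest objection is one of scope, and it stands. A reader might infer from the requirement of 64 per group, set against the 60 exposed live births expected in section 9.5, that the study cannot reach 80% power at 0.5 SD without adjustment. The protocol does not support that. The 64 applies to equal groups only. Section 9.5 expects 60 exposed live births and 120 in each comparison group, and within those numbers unadjusted t-test power is 80.2% for 48 vs 96, 80.3% for 60 vs 69 and 88.2% for 60 vs 120. Table 3 is also titled as based on a minimal sample size, and section 9.2.2 continues recruitment for 10 years even if 75 exposed pregnancies are reached earlier. What fails is the fixed 40/40 design.

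A second objection is that adjustment rescues the figure. Section 9.4.5.2 collects the WASI-II from the mother or primary caregiver to help interpret group differences, and section 9.7.2.5.2 already provides for adjusted estimates by linear regression with 95% confidence intervals. Some power may be recovered this way. The amount depends on a correlation the protocol does not state. The usual variance-reduction formula also assumes a covariate balanced between groups, whereas this is a non-randomised registry whose section 9.9 expects the groups to differ. The adjustment cannot support the 80%.

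Third, section 9.9 already concedes that the modest sample limits power for primary and secondary endpoints, and the protocol nowhere says that a null Phase II result would exclude a half-SD deficit. Both are true. They temper the consequence, but a general caution does not correct a specific figure.

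**Conclusion.** The power in the Phase II row of Table 3 is wrong as written. With 40 vs 40 children, two-sided alpha 0.05 and separate comparisons, power at 0.5 SD is about 60% instead of 80%, and the difference detectable with 80% power is about 0.63 SD instead of 0.5 SD. This rests on an unadjusted two-sample comparison of means, and no reading consistent with the protocol's own conditions restores 80%.

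The 0.5 SD is established by Table 3. Section 9.4.5.2 is affected because it repeats the 0.80 at the same size. The error touches one part of one secondary outcome, tested in a subset of children. The primary endpoint's power row and analysis do not depend on it.

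**What to change.** - In Table 3, restate the Phase II row either as about 60% power at 0.5 SD, or as 0.63 SD at 80% power, with 40 per group.
- In section 9.4.5.2, make the power statement agree with the corrected row and give the effect size it refers to.
- If the 60% figure is chosen, except this row from the statement in section 9.5 that the Table 3 effects are detectable at 80% power or more.
- Do not cite adjustment for the caregiver WASI-II score in support of the 80%.

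This is a wording change and needs no additional children or testing. Its one downside is a less favourable stated figure.

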9.4.6 Dysmorphology Evaluation

All live born infants will be examined by one of a team of study-dedicated dysmorphologists, led by a co-investigator from the University of California, San Diego. All members of the team are licensed pediatricians with subspecialty fellowship training in dysmorphology and/or genetics. This team of physicians has been functioning as the specialist examiners for the current MotherToBaby/OTIS Pregnancy Studies and have completed examinations for well over **1400** infants throughout North America as part of this protocol using the same standard procedures as are incorporated in this Registry. The physical examinations evaluate infants for both major and minor structural **birth** defects which provide increased sensitivity for detecting a specific pattern of malformation should one exist. All infants will be examined as soon as is practical, and optimally within the first year of life. The Research Center will group and schedule these follow-up examinations to maximize physician blinding as to exposure status, and to minimize travel time and expense for these types of investigations.

Infant examinations will be conducted using a standard checklist of approximately 130 minor malformations included in a dysmorphology exam form (see [Appendix A, 04.E. Dysmorphology Exam Form](#)). In addition, digital photographs of the infant will be taken to aid in validating any diagnoses.

9.4.7 Biological Assessment of Child Immune Function

To supplement the information obtained on serious infections and hospitalizations and vaccination experience over the 5-year follow-up period for all live born children in the study, a biological sample sub-study will be offered to **subjects** in all 3 cohorts, to be overseen by a co-investigator. Eligible infants will be **at least 6 months of age, and preferably by 12 months of age** and will have had up to 3 diphtheria, tetanus, and pertussis scheduled immunizations. A small blood sample via heel stick **or venipuncture** will be collected in enrolled infants and sent to a single laboratory for analysis of IgG-tetanus antibody. Results of the test will be measured both continuously as well as classified as negative, indeterminate, or positive.

OTIS will communicate the result to the mother, and in those situations where the result is negative or indeterminate, the mother will be advised to share this result with her pediatrician, and OTIS will recommend repeating the test in approximately 1 year. The expectation is that near 100% of children in all 3 groups will test positive for immunity.

As this sample collection is most efficiently accomplished at the **contracted laboratory, the study will work with subjects to identify a local laboratory location for sample collection. If the subject is unable or unwilling to have the sample taken at the contracted laboratory, the sample may be taken at the** time of the dysmorphology examination. The study physicians will be tasked with collecting samples from infants whose mothers have consented. The dysmorphology exam for this study will be scheduled preferentially at or after 6 months of age and should coincide with the adequacy of immune response assessment. In the case where the dysmorphology exam is scheduled prior to 6 months, an additional appointment **may** be scheduled in order to collect samples for the adequacy of immune response assessment 6 to 12 months after delivery. **If it is not possible for the subject to have the sample taken by the contracted laboratory or the study dysmorphologist, the study will work with the subject to coordinate with the child's pediatrician or the laboratory associated with the pediatrician's office to collect the sample.**

While it is anticipated that not all mothers will agree to this sub-study, a sample size of 60 in each group will be targeted, with preference given to recruiting exposed pregnancies that represent the distribution of length of exposure.

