9.3.2.2.2 Infant Outcomes

- Rate and pattern of minor structural **birth** defects where a minor structural **birth** defect is defined as a structural anomaly (itemized on the study examination form) which has neither cosmetic nor functional significance to the child, and a pattern is defined as the same 3 or more minor structural **birth** defects in 2 or more children (see [Appendix A](#), 04.E. Dymorphology Exam Form). Due to the large variability in the sensitivity and specificity of identification of minor defects, in this study, minor defects are tabulated only in those infants who receive the study-related physical examination. This approach of assessment for clusters is based on prior studies that suggest 3 or more minor malformations is a meaningful cut point ([Leppig et al, 1987](#); [Méhes et al, 1973](#); [Marden et al, 1964](#)).
- Rate of small for gestational age where small for gestational age is defined as birth size (weight, length, or head circumference) \leq 10th centile for sex and gestational age using standard pediatric CDC growth curves for full term or preterm infants ([NCHS, 2000](#); [Olsen et al, 2010](#)).
- Rate of postnatal growth deficiency where postnatal growth deficiency is defined as postnatal size (weight, length, or head circumference) \leq 10th centile for sex and age using standard pediatric growth curves, and adjusted for postnatal age for premature infants if the postnatal measurement is obtained at less than 1 year of age.
- Rate of postnatal serious infections (see [Appendix D](#)) and hospitalizations as assessed throughout the 5-year postnatal follow-up period. Pediatric records will be requested after delivery and then on an annual basis with specific requests for documentation of serious infections and hospitalizations
- Rate of infant reactions to scheduled vaccinations as assessed throughout the 5-year postnatal follow-up period. Pediatric records and a questionnaire regarding vaccine administration according to recommended schedule and any vaccine-related adverse events will be obtained on an annual basis (see [Appendix A](#), 08.12. Vaccine Information Form).
- Infant response to IgG-tetanus antibody as a biological marker to evaluate humoral immune response. To be performed via a heel stick **or venipuncture** and standardized assay test between 6-12 months of age in a subset of infants in each of the study groups, conditional on the consent of the mother.

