9.7.2.4.1 Description of Study Enrollment

Outcome	Analysis Subset
Major Structural Birth Defect Among Live Births	All pregnancies ending in at least 1 live born infant
Major Structural Birth Defects Among All Pregnancies Excluding Lost to Follow-Up	All pregnancies excluding lost to follow-up
Spontaneous Abortion	Pregnancies enrolled prior to 20 weeks' gestation
Stillbirth	Pregnancies enrolled excluding lost to follow-up
Preterm Delivery	Pregnancies enrolled prior to 37 completed weeks' gestation, excluding pregnancies ending in twin or higher order multiple births
Minor Structural Birth Defects	Live born infants who have received the dysmorphology examination
Small for Gestational Age Infants	Live born infants excluding twin or higher order multiple births
Breastfeeding	Pregnancies ending in at least 1 live born infant
Postnatal Growth	Live born infants followed up to 1 year postpartum, excluding twin or higher order multiple births
Serious or Opportunistic Infections	Live born infants followed up to 1 year postpartum
Immune Function	Live born infants who received the tetanus titer testing
Response to vaccines	Live born infants who received at least one vaccine
Neurodevelopment	Live born infants for whom developmental screening questionnaires were completed or face-to-face testing was completed

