9.7.2.5.2 Secondary Analysis

The following will comprise the secondary analyses:

1. Comparison of all secondary outcomes between the Specific Evolocumab-Exposed cohort and Comparison Group I
2. Comparison of the primary and all secondary outcomes between the Specific Evolocumab-Exposed cohort and Comparison Group II

The comparison of the prevalence of the total proportion of major structural **birth** defects between the Specific Evolocumab-Exposed cohort and Comparison Group II will be among all live births and, separately, among all pregnancies excluding those lost to follow-up. The comparison of the prevalence of ≥ 3 minor malformations between the Specific Evolocumab-Exposed cohort and each of the 2 comparison groups will be among children who receive the dysmorphological examination. The comparison of IgG-tetanus antibody status (test negative or indeterminate vs test positive) by group (Exposed, Comparison Group I, Comparison Group II) among those in the biological sample sub-study.

In each cohort we will separately calculate the proportion of all pregnancies ending in live birth, spontaneous abortion, stillbirth, elective termination, and lost to follow-up; crude comparisons will be made between cohorts.

The evaluation for a pattern of minor structural **birth** defects will be conducted using the following steps:

1. A comparison among groups of the proportion of infants with any 3 or more minor structural **birth** defects will be made without regard to pattern
2. Among infants with 3 or more minor **structural birth** defects, the Evolocumab-Exposed group will be examined for evidence of a specific pattern of 3 or more defects in any 2 or more children. If such a pattern is identified, Comparison Groups I and II will be evaluated for any evidence of the same pattern.

In each cohort among all live born infants we will separately calculate the proportion of premature delivery, small for gestational age on weight, length or head circumference, and rates of serious infections, hospitalizations, adverse vaccine reactions, and adverse neurodevelopmental outcomes; crude comparisons will be made between cohorts.

Mean birth weight, length and head circumference for full-term live born infants will be compared between cohorts. Postnatal growth parameters will be compared using the proportion of infants ≤ 10 th centile for sex and age with respect to weight, height, or head circumference.

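### The tetanus-antibody endpoint sets no minimum number of tetanus doses, so a negative or indeterminate titer in an un- or under-vaccinated infant is counted as an inadequate immune response

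*Protocol*

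**What the plan says.** Protocol 9.3.2.2.2 gives the purpose of the test: "Infant response to IgG-tetanus antibody as a biological marker to evaluate humoral immune response".

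Eligibility is in 9.4.7. The vaccination condition is that infants "will have had up to 3 diphtheria, tetanus, and pertussis scheduled immunizations". The age condition is "at least 6 months of age, and preferably by 12 months of age". The same section adds that "Results of the test will be measured both continuously as well as classified as negative, indeterminate, or positive", and it expects close to 100% of children in all three groups to test positive.

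The analysis subset for Immune Function in 9.7.2.4.1 is "Live born infants who received the tetanus titer testing". The next row of that table, Response to vaccines, is conditioned on vaccination: "Live born infants who received at least one vaccine".

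Section 9.7.2.5.2 defines the contrast: "The comparison of IgG-tetanus antibody status (test negative or indeterminate vs test positive) by group". Table 3 in 9.5 plans the endpoint with 60 exposed and 120 comparison infants, a 20% baseline rate of inadequate response, a relative risk of 2 and 82% power. A footnote explains the 120 as an estimate of 60 infants per cohort.

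**The concern.** A tetanus titer shows how well an infant responds to vaccination only if the infant has been vaccinated. Read literally, 9.4.7 admits infants with 0, 1 or 2 doses, and 9.7.2.4.1 analyses all of them. Neither section sets a minimum number of doses or an interval from the last dose to the sample. Sampling is tied to age and to a convenient visit. A negative or indeterminate result can then mean a failed response, a missing vaccination or an incomplete series, and the endpoint cannot tell these apart.

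Humoral immune suppression is one of the potential safety signals named in the background (sections 4 and 7), and this titer is its only laboratory measure. If uptake is equal across groups, the extra negatives push the relative risk towards 1 and hide a true effect. If uptake differs, they can produce a difference without any drug effect. Equal uptake cannot be presumed: section 9.9 itself acknowledges selection, differences in disease severity and possible imbalance in unintended pregnancy.

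**Working it through.** **Inputs from the protocol.** Table 3: 60 vs 120 infants, baseline 20%, relative risk 2 (so 40% vs 20%), two-sided alpha 0.05, power 82%. Section 9.4.7: nearly all children expected to test positive.

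**Assumptions, because the documents give no uptake figure.** A share u of tested infants is undosed, and undosed infants test negative. Among vaccinated infants the inadequate rate r is either the Table 3 planning rate (20%) or 2%, which is one reading of the near-complete positivity expected in 9.4.7.

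**Step 1: the plan's own figure.** Pooled-variance normal approximation:

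- pooled rate = (60×0.40 + 120×0.20)/180 = 0.267
- null SE = √[0.267×0.733×(1/60 + 1/120)] = 0.0699
- alternative SE = √(0.40×0.60/60 + 0.20×0.80/120) = 0.0730
- z = (0.20 − 1.96×0.0699)/0.0730 = 0.86, so power is 80.6%

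This is within two points of the stated 82%. With a single comparison cohort of 60 the same formula gives 67.0%.

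**Step 2: equal under-vaccination.** Observed rate = u + (1 − u)×r. With r = 40% vs 20%:

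| u, both groups | Exposed | Comparison | Observed RR | Power, 60 vs 120 |
|---|---|---|---|---|
| 0% | 0.40 | 0.20 | 2.00 | 80.6% |
| 5% | 0.43 | 0.24 | 1.79 | 73.7% |
| 10% | 0.46 | 0.28 | 1.64 | 66.8% |
| 20% | 0.52 | 0.36 | 1.44 | 53.8% |

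With r = 4% vs 2% (true relative risk again 2), u of 5%, 10% or 20% leaves an observed relative risk of 1.28, 1.15 or 1.07.

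**Step 3: unequal under-vaccination, no drug effect.** Comparison group 5% undosed; r the same in both groups. Rejection is by two-sided Fisher's exact test, 60 vs 120:

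| Undosed, exposed | r = 20%: RR (rejection) | r = 2%: RR (rejection) |
|---|---|---|
| 10% | 0.28/0.24 = 1.17 (7.7%) | 0.118/0.069 = 1.71 (16.8%) |
| 15% | 0.32/0.24 = 1.33 (18.3%) | 0.167/0.069 = 2.42 (46.9%) |
| 20% | 0.36/0.24 = 1.50 (35.1%) | 0.216/0.069 = 3.13 (76.2%) |

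Against one comparison cohort of 60, the rejection rates are 5.1%, 11.8% and 23.4% at r = 20%, and 8.1%, 28.0% and 55.2% at r = 2%.

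**Step 4: if only half of undosed infants test negative.** Observed rate = 0.5u + (1 − u)×r. For u = 10% in both groups at Table 3 rates: (0.05 + 0.36)/(0.05 + 0.18) = 0.41/0.23 = 1.78. For 10% vs 5% undosed at r = 2%: (0.05 + 0.018)/(0.025 + 0.019) = 0.068/0.044 = 1.55. The direction is unchanged and the size is smaller.

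**Step 5: excluding undosed infants instead of keeping them.** At 40% vs 20% and the Step 1 formula, removing 5%, 10% or 20% leaves 57 vs 114, 54 vs 108 or 48 vs 96, with power 78.6%, 76.5% or 71.7%. Keeping them gives 73.7%, 66.8% or 53.8% (Step 2).

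**The case against.** The best defence is that the eligibility phrase describes infants vaccinated on schedule, who by this age have had as many as three doses. The expectation of almost universal positivity in the same section supports that reading, since it presupposes vaccination. This stands as a view of intent, but the sentence does not say it, and neither does the analysis subset.

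A second defence is that the data are not lost. Vaccine administration is requested annually (9.3.2.2.2, 9.4.4), the titer is also kept as a continuous value, and 9.7.2.5.2 foresees adjustment for potential confounders. That makes the problem repairable at analysis. It does not remove it, because the adjustment language is generic and the protocol itself fixes the subset as everyone tested. A SAP that follows 9.7.2.4.1 inherits the rule.

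A reader might also infer three stronger things that the documents do not support:

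- That every unvaccinated infant is scored as inadequate. Classification follows the test result ("test negative or indeterminate vs test positive"), so this happens only if the titer is negative or indeterminate.
- That the endpoint measures uptake in place of immune function. It mixes the two. Uptake dominates only if inadequate response among vaccinated infants is very rare, and much less at the 20% planning rate.
- That 10% against 5% undosed alone (6/60 vs 3/60, relative risk 2.0) reproduces the effect Table 3 is built to detect. Table 3 contrasts 40% with 20%; at its baseline, the same imbalance gives 1.17.

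**Conclusion.** The point holds as a defect in stated rules. Eligibility has no minimum dose, the subset has no vaccination condition, and together with the chosen dichotomy they count some missing or incomplete vaccination as immune failure. The bias can run either way: towards no effect when uptake is equal, and in either direction when it is not.

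Its size is unknown, because it rests on an undosed share that the documents do not give and on the assumption that undosed infants test negative. Over 5% to 20% undosed in both groups, the planned relative risk of 2.0 falls to between 1.79 and 1.44. With 10% vs 5% undosed and no drug effect, the spurious relative risk lies between 1.17 (20% inadequate among vaccinated) and 1.71 (2%).

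Severity is moderate. This is one secondary endpoint in a voluntary sub-study, the primary outcome is untouched, and serious infections are followed clinically for five years besides.

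**What to change.** - In 9.7.2.4.1, restrict the Immune Function subset to infants with documented tetanus vaccination before the sample: at minimum one dose, in line with the Response to vaccines row.
- In 9.4.7, reword the eligibility phrase so that it states the same condition.
- Adjust or stratify both the dichotomous comparison and the continuous titer by number of doses and time since last dose. A one-dose minimum alone still leaves partly vaccinated infants in the comparison. Use the pediatric records and the Vaccine Information Form, after confirming that the form captures dose dates; its content is not in the protocol.
- List tested infants outside the subset separately.

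Requiring a completed primary series and rescheduling samples around it would be stricter, but it discards infants with one or two doses and is a matter of choice. It is not needed to remove the main defect.

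The change concerns the analysis set and wording only; no child's vaccinations are affected. The cost is a slightly smaller analysed number, and there is no reserve in the exposed group, since section 9.5 expects only 60 exposed live births and the sub-study targets 60. At Table 3 rates, excluding 10% undosed leaves about 76.5% power, against 66.8% if they stay in and test negative.
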